2.4 SECONDARY OUTCOME MEASURES

2.4.1 Secondary Effectiveness Outcome Measures

- Progression free survival (PFS) at 2 and 3 years, defined as the time from the date of treatment initiation until the first documented progression of disease measured by routine clinical care or death from any cause, whichever occurs first. Patients who have no disease progression and have not died or who are lost to follow-up at the time of analysis will be censored at the date of last tumor assessment where no progression was documented or the last date of follow-up for disease, whichever is last. Patients without post-baseline tumor assessments will be censored at the time of their baseline visit unless death occurs prior to their first scheduled tumor assessment;
- Time to next treatment (TTNT), defined as the Time to initiation of subsequent systemic anti-cancer therapy following initiation of Obinutuzumab containing therapy. Patients not starting a subsequent systemic anti-cancer therapy will be censored at the date of the last study visit;
- Overall survival (OS), defined as the time from initiation of study treatment to death from any cause. Patients who still alive at the time of analysis and patients who are lost to follow-up will be censored at their last time known to be alive;
- Correlation between POD24 and OS;
- TTLCB, defined as the time from first dose to loss of clinical benefit as assessed by the treating physician (single or multiple reasons possible: e.g. disease progression, deterioration in ECOG PS, death, other). Patients who do not loss clinical benefit will be censored at the date of the last study visit. Patients without post-baseline tumor assessments will be censored at the time of their baseline visit unless death occurs prior to their first scheduled tumor assessment;
- Overall response rate (ORR);
- Complete response (CR);
- Complete response at 30 months (CR30);

- Duration of response (DoR) measured per clinical practice, defined as the time from first documentation of CR or partial response (PR) (whichever occurs first) until disease progression, as evaluated by the physician according to routine clinical practice or death. Patients who have no disease progression and have not died or who are lost to follow-up at the time of analysis will be censored at the date of last tumor assessment where no progression was documented or the last date of follow-up for disease, whichever is last;
- Time to response, defined as the time from first dose of Obinutuzumab to first documented response as assessed in clinical routine. Patients without response at the time of analysis and patients who are lost to follow-up will be censored at the date of their last tumour assessment. Patients without post-baseline tumor assessments will be censored at the time of their baseline visit unless death occurs prior to their first scheduled tumor assessment;
- Rate of patients with stable disease (SD);
- Effectiveness of Obinutuzumab in different patient subgroups, stratified by FLIPI (intermediate/high), ECOG-PS, age at study entry, hepatitis infection (history of past/resolved infection or latent HBV after prophylaxis as per standard treatment guidelines), chemotherapy backbone choice, presence of autoimmune disease, history of renal failure and liver failure.

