- To evaluate the safety of Obinutuzumab in a real-world setting.

Other Objectives

- To describe the treatment pattern in first and second line of treatment;
- To evaluate methods applied to tumor and response evaluations according to used guidelines and clinical practice;
- To evaluate the FDG-PET response at end of induction and end of maintenance, as per clinical practice;
- To evaluate the Quality of life;
- To evaluate the presence of B symptoms;
- *To explore effectiveness of Obinutuzumab in real world setting*
- *To explore prescription profile*
- *To explore COVID-19 impact on therapy adherence*

Study Design

This is a retrospective and prospective primary data collection and secondary data use, non-interventional, multi-centre study designed to assess real-world effectiveness and safety of Obinutuzumab in previously untreated advanced FL patients, prescribed in first line with Obinutuzumab and chemotherapy, according to existing label.

The study will be conducted in approximately 50 Italian centres distributed all across the country and will collect data during treatment with Obinutuzumab and up to 3.5 years following the start of the treatment. Enrolment will be competitive across sites. Since the study is observational, the treating physician will make all treatment decisions according to his/her regular practice independent of this study. No treatment regimen is mandated by this protocol. Patients should be included after the start of treatment, including newly diagnosed FL patients. Patients included should have performed at least 2 cycles of induction treatment with Obinutuzumab and chemotherapy within 1 year from beginning of treatment.

During the treatment with Obinutuzumab, patient data will be collected at the clinical visits planned by the treating physician, including retrospective data of cycles performed before enrolment, baseline data and medical history. The collection of retrospective data will be those generated from the start of treatment with Obinutuzumab to study entry.

After cessation of Obinutuzumab treatment, patient data will be collected approximately every 3-6 months, as part of routine clinical practice visits, or remote contact, until lost to follow-up, withdrawal of consent or death, for up to 3.5 years following start of Obinutuzumab treatment. Follow-up data will include at least tumor assessments, *new anti-lymphoma therapy informations*, and safety data.

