6.3.2 Secondary Effectiveness Variable

- Progression free survival (PFS) at 2 and 3 years, defined as the time from the date of treatment initiation until the first documented progression of disease measured by routine clinical care or death from any cause, whichever occurs first. Patients who have no disease progression and have not died or who are lost to follow-up at the time of analysis will be censored at the date of last tumor assessment where no progression was documented or the last date of follow-up for disease, whichever is last. Patients without post-baseline tumor assessments will be censored at the time of their baseline visit unless death occurs prior to their first scheduled tumor assessment;
- Time to next treatment (TTNT), defined as the Time to initiation of subsequent systemic anti-cancer therapy following initiation of Obinutuzumab containing therapy. Patients not starting a subsequent systemic anti-cancer therapy will be censored at the date of the last study visit;
- Overall survival (OS), defined as the time from initiation of study treatment to death from any cause. Patients who still alive at the time of analysis and patients who are lost to follow-up will be censored at their last time known to be alive;
- Correlation between POD24 and OS;
- TTLCB, defined as the time from first dose to loss of clinical benefit as assessed by the treating physician (single or multiple reasons possible: e.g. disease progression, deterioration in ECOG PS, death, other). Patients who do not loss clinical benefit will be censored at the date of the last study visit. Patients without post-baseline tumor assessments will be censored at the time of their baseline visit unless death occurs prior to their first scheduled tumor assessment;
- Overall response rate (ORR);
- Complete response (CR);
- Complete response at 30 months (CR30);
- Duration of response (DoR) measured per clinical practice, defined as the time from first documentation of CR or partial response (PR) (whichever occurs first) until disease progression, as evaluated by the physician according to routine clinical practice or death. Patients who have no disease progression and have not died or who are lost to follow-up at the time of analysis will be censored at the date of last tumor assessment where no progression was documented or the last date of follow-up for disease, whichever is last;

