Severity and seriousness need to be independently assessed for each AE recorded on the CRF (for detailed instructions, see Appendix 3).

Adverse Events of Special Interest AEs of special interest for this study include the following:

- *Tumor lysis syndrome (TLS), irrespective of causality*
- *Second malignancies*
- *Cases of potential medicine-induced liver injury that include an elevated ALT or AST in combination with either an elevated bilirubin or clinical jaundice, as defined by Hy's law (see Appendix 3).*
- *Suspected transmission of an infectious agent by the study medicine, as defined below:*
Any organism, virus, or infectious particle (e.g., prion protein transmitting transmissible spongiform encephalopathy), pathogenic or non-pathogenic, is considered an infectious agent. A transmission of an infectious agent may be suspected from clinical symptoms or laboratory findings that indicate an infection in a patient exposed to a medicinal product. This term only applies when a contamination of the study medicine is suspected

~~Serious IRRs;~~

~~Tumour lysis syndrome (irrespective of regulatory seriousness criteria);~~

~~Serious neutropenia~~

~~Serious infections;~~

~~Hepatitis B reactivation while receiving the appropriate anti-viral therapy.~~

Non-Serious Adverse Events other than Adverse Events of Special Interest

All non-serious AEs (in addition to AEs of special interest) must be collected according to the appropriate level of MedDRA classification.

The physicians are reminded of the possibility to report any adverse reactions (for which they suspect a causal role of a medicinal product) that come to their attention to the

marketing authorization holder of the suspected medicinal product, or to the concerned competent authorities via the national spontaneous reporting system.

The Marketing Authorization Holder is responsible to submit adverse reactions to the competent regulatory authority.

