Data Collection (available data will be collected; no additional diagnostic or monitoring procedures will be applied to patients outside of routine clinical practice)	Enrolment visit ^a	Retrospective Data collection	Prospective Data Collected during Treatment Period (Induction and maintenance period)	Follow-up period ^b
Informed consent ^c	x			
Diagnosis confirmation (clinical stage, histology)		x		
Target Population	x	x		
Medical history and demographic data		x		
Concomitant treatments/medications ^d	x	x	x	
Treatment with Obinutuzumab	(x) ^e	(x) ^c	x	
Prophylaxis medication	x	x	x	
Laboratory assessments ^e	x	x	x	
Pregnancy test	x ^f	x ^f	x ^f	
Physical examination and Vital signs	x	x	x	
ECOG	x	x	x	x
B symptoms	x	x	x	x
QoL (Quality of life: EuroQol 5-Dimension Questionnaire, 5-level version (EQ-5D-5L); Functional Assessment of Chronic illness Therapy-Lymphoma (FACT-Lym) ^g	x		x	*
Chemotherapy regimen	x	x	x	
AEs/SAEs/AESI/SSIRR/ADR	x		x	x ^k
Retrospective Safety data collection		x ^h		
Tumor assessments	x	x	x	x
Ann Arbor	x	x		
FLIPI score assessment ⁱ	x	x		
BM evaluation	x	x	x	x
Response rate ^j	x	x	x	x
New anti-cancer therapy and survival status after end of treatment				x

^a Items Concomitant treatments/medications, Treatment with obinutuzumab, Pregnancy test. Physical examination and Vital signs, Prophylaxis medication and Chemotherapy regimen apply only for patients still on treatment at the time of enrollment as part of their standard procedures for treatment. In case of patients

enrolled after treatment completion, these data will be collected as indicated in the Retrospective column and the prospective information will be collected as described in the Follow-up period.

^b Approximately one-year follow-up after last dose of Obinutuzumab administration, as per clinical practice, or for patients that early discontinue the treatment up to 3.5 years after first treatment administration or until withdrawal of consent, study termination by the Sponsor, or death, whichever occurs first, regardless of whether patients start a new anti-cancer therapy. For patients that discontinue treatment before completing induction or maintenance, the follow up parameters can be collected in accordance with current patient's schedule visit and not every 2 months. Follow-up data will include at least tumor assessments, *new anti-lymphoma therapy informations*, and safety data.

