2.5 OTHER OUTCOME MEASURES

Other variables of interest are below:

- Patient/disease characteristics: age, sex, ECOG PS, Ann Arbor staging, FLIPI (intermediate/high), medical history and history of FL, comorbidities, physical examination and vital signs;
- Treatment pattern:
 - Time from diagnosis to start of treatment with Obinutuzumab;
 - Duration of treatment with Obinutuzumab;
 - Dose modifications;
 - Treatment discontinuation;
 - Prophylaxis medications;
 - Type of chemotherapy chosen in association with Obinutuzumab;
 - Second line regimens prescribed for patients who progressed within two years after starting first line therapy;

- Time to initiation of subsequent systemic anti-lymphoma therapy following initiation of Obinutuzumab containing therapy;
- Adherence to treatments
- Quality of life: EuroQol 5-Dimension Questionnaire, 5-level version (EQ-5D-5L); Functional Assessment of Chronic illness Therapy-Lymphoma (FACT-Lym);
- Presence of B symptoms;
- Concomitant medication prescribed or in current use from the start of therapy with Obinutuzumab until discontinuation of the treatment;
- FDG-PET response at end of induction and end of maintenance, as per clinical practice. When PET is not performed, the alternative routine tumor assessment method will be collected;
- Differences in patient/disease characteristics and treatment pattern/adherence pre- and post- COVID19 pandemic.

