3.2.2 Secondary Outcome Measures

Time-to-event outcomes (PFS at 2 and 3 years, TTNT, OS, TTLCB, duration of response, and time to response) will be analyzed according to the survival analysis methods. The quartiles with their 95% confidence interval (estimated using Kaplan-Meier methods and Greenwood's formula) will be presented. Kaplan-Meier plots with a 95% CI will be prepared. Estimates for the survivor functions for all time to event endpoints will be obtained by the Kaplan-Meier approach.

Cox regression analysis will be used to assess which variables are predictive of OS as well as to evaluate the association between early POD and OS from a risk-defining event, that is, survival from time of POD for early progressors or from 2 years after diagnosis.

Response rates (ORR, CR, CR30 and rate of patients with stable disease) will be presented with the number and proportions of responders and non-responders together with two-sided, 95% Clopper-Pearson CIs.

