3.4 SENSITIVITY ANALYSES

No sensitivity analyses are planned.

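### TTNT ends at any systemic anti-cancer therapy, while the matching treatment-pattern interval ends at anti-lymphoma therapy, and deaths before next therapy are censored at the last visit

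*SAP*

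**What the plan says.** SAP 2.4.1 gives the secondary endpoint as "Time to next treatment (TTNT), defined as the Time to initiation of subsequent systemic anti-cancer therapy following initiation of Obinutuzumab containing therapy". Protocol 6.3.2 and the Synopsis define it the same way. The only censoring rule, identical in both documents, is "Patients not starting a subsequent systemic anti-cancer therapy will be censored at the date of the last study visit". It mentions neither death nor therapy for another cancer.

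SAP 2.5 and Protocol 6.3.4 list under treatment pattern "Time to initiation of subsequent systemic anti-lymphoma therapy following initiation of Obinutuzumab containing therapy". The start and sentence form match TTNT; the type of therapy differs, and no censoring rule is given.

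Data collection is split in the same way. The Protocol Synopsis and Appendix 2 (note b) require follow-up to include at least "new anti-lymphoma therapy informations". The Appendix 2 schedule row, repeated in SAP Appendix 1, is "New anti-cancer therapy and survival status after end of treatment", and Protocol 6.5.2 also speaks of anti-cancer therapy.

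Protocol 8.1.1.2 lists "Second malignancies" among the adverse events of special interest. SAP 3.2.2 puts TTNT with the endpoints analysed by Kaplan-Meier, and SAP 3.4 says "No sensitivity analyses are planned".

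**The concern.** TTNT is listed among the effectiveness outcomes, where a reader will take an event to mean that first-line lymphoma treatment no longer sufficed. The wording lets in two things that do not fit.

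First, a patient in lymphoma remission who starts systemic therapy for a different cancer has an event. That is a safety outcome counted against effectiveness.

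Second, a patient who dies before any next therapy, including one dying of progressing lymphoma, is censored like a patient in remission. Kaplan-Meier then treats that patient as someone who could still be retreated later.

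The report may also carry two times to next therapy from the same first dose, one in the effectiveness results and one in the treatment-pattern summary, with nothing to explain a difference. Sites that record only the stated minimum may omit treatment of other cancers, while sites that follow the schedule row would record it. With about 50 sites, the TTNT event could depend on which passage a site followed.

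**Working it through.** **The plan's own figures.** The documents give no figure for TTNT. The precision statements concern POD24 and 3-year PFS with n = 300. The Clopper-Pearson limits are the 2.5% quantile of Beta(x, n − x + 1) and the 97.5% quantile of Beta(x + 1, n − x).

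- POD24 13%, x = 39: 9.4% to 17.3%, width 7.93 points (stated 7.9).
- 3-year PFS 80%, x = 240: 75.0% to 84.4%, width 9.36 points (stated 9.4).

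Both reproduce, and neither depends on the TTNT wording.

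**The definitions side by side.**

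| | TTNT (SAP 2.4.1, Protocol 6.3.2) | Treatment pattern (SAP 2.5, Protocol 6.3.4) |
|---|---|---|
| Start | Initiation of obinutuzumab-containing therapy | Same |
| Event | Systemic anti-cancer therapy | Systemic anti-lymphoma therapy |
| Therapy for another cancer | Not excluded | Outside the wording |
| Death before therapy | Censored at last visit, as a patient who did not start therapy | No rule |

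**Effect of one patient.** If the patient would not otherwise have had an event, therapy for another cancer adds 1/300 = 0.33 points to the crude event proportion.

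**Illustration only.** Both rates here are assumptions. Let L be the proportion starting lymphoma therapy by 42 months and S the proportion starting systemic therapy for another cancer. Take independent exponential hazards and ignore deaths and dropout. Then:

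- Proportion with any event = 1 − (1 − L)(1 − S), so the increase over L is S(1 − L).
- Share of events due to other cancers = ln(1 − S) / [ln(1 − L) + ln(1 − S)].

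| L | S | Any event | Increase (points) | Share from other cancers | Such events in 300 |
|---|---|---|---|---|---|
| 10% | 1% | 10.9% | 0.90 | 8.7% | 2.8 |
| 10% | 5% | 14.5% | 4.50 | 32.7% | 14.2 |
| 15% | 3% | 17.55% | 2.55 | 15.8% | 8.3 |
| 20% | 1% | 20.8% | 0.80 | 4.3% | 2.7 |
| 20% | 5% | 24.0% | 4.00 | 18.7% | 13.5 |

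Over L = 10% to 20% and S = 1% to 5%, the increase runs from 0.8 to 4.5 points and the share from about 4% to 33%. The width of that range shows how little can be said without real rates.

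**Deaths.** With deaths censored, one minus Kaplan-Meier estimates the probability of next therapy as if death did not remove patients from risk. It is therefore never below, and generally exceeds, the proportion who actually start next therapy. The gap grows with the number of deaths before retreatment. The documents give no such number, so only the direction can be stated.

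**The case against.** The strongest reply is that the authors used the two terms interchangeably. The minimum follow-up data name lymphoma therapy, while the schedule row covering that follow-up names cancer therapy. Protocol 6.5.2 mentions anti-cancer therapy after first line, which reads like lymphoma lines of treatment. This stands as a possibility. It rules out saying that the endpoint is known to mix other cancers in, and leaves a literal reading that nothing in either document overrides. If the terms are synonyms, one still has to be corrected.

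The lymphoma-specific interval is indeed already listed. But it sits with the other outcome measures, has no censoring rule, and is not the quantity labelled TTNT in the effectiveness outputs.

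Lymphoma deaths are also counted elsewhere: in POD24 if within 24 months, in PFS and OS, and as a possible reason for loss of clinical benefit. That limits the damage to TTNT but does not make the TTNT curve correct.

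A reader might infer two stronger things, and the documents support neither:

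- **That second malignancies are expected in some number.** Listing as an event of special interest shows interest, not frequency; the same list includes suspected transmission of an infectious agent by contaminated study medicine.
- **That 13% POD24 and 20% 3-year PFS failure (39 and 60 of 300) can stand in for retreated patients.** PFS includes deaths from any cause, progression is not retreatment, and the two figures refer to different time points. A share of TTNT events built on them has no basis in the plan.

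**Conclusion.** The inconsistency is real. Applied as written, the TTNT rule counts systemic therapy for another malignancy as an event and censors deaths before next therapy, and no sensitivity analysis would reveal either effect. Whether the authors intended this cannot be settled from the documents.

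The size is unknown. The firm figure is at most 0.33 points per affected patient; the 0.8 to 4.5 point range rests wholly on assumed rates and independent hazards.

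TTNT is a secondary measure in a study without hypothesis tests, and POD24, PFS, OS and the sample size do not depend on it. The change is worth making because it is specific and cheap, not because the main conclusions are at risk.

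**What to change.** 1. In SAP 2.4.1 and Protocol 6.3.2 (and the Synopsis), define the TTNT event as the first subsequent systemic anti-lymphoma therapy, matching SAP 2.5 and Protocol 6.3.4. Use this one definition wherever time to next therapy is reported.
2. State that systemic therapy for another malignancy is not a TTNT event.
3. Report the cumulative incidence of next anti-lymphoma therapy with death as a competing event, alongside or in place of the Kaplan-Meier curve.
4. Align the therapy wording in the follow-up text and the schedule row, and confirm that the eCRF lets the regimen or indication of each new therapy be identified.

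The cost is a wording change in both documents and one extra curve. Protocol section 3 requires approval for changes that are not purely logistical or administrative, so the protocol edit may need ethics committee approval. The eCRF is not among the documents, so whether it already captures the indication has to be checked; if it does not, sites would have to supply it.

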For each patient, the study will consist of a period of 42 months which can include: an induction treatment period (approximately 6 months) in which patients will receive Obinutuzumab and chemotherapy followed by a maintenance treatment period (approximately 24 months) in which patients will receive Obinutuzumab monotherapy and a follow-up period of one year, after the last Obinutuzumab administration. Patients will be followed for 3.5 years after the first treatment administration regardless of early discontinuation of treatment for any reason in any timepoint. Patients who discontinue treatment for reasons other than disease progression (e.g., toxicity, AE) will continue to have their data collected for tumor assessments performed as per clinical practice, until disease progression, withdrawal of consent, study termination by the Sponsor, or death, whichever occurs first, regardless of whether patients start a new anti-cancer therapy.

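### Time to response: Kaplan-Meier censors patients who progress or die without responding, so the top of the curve can sit slightly above the proportion who respond, by about 1 point under the protocol's planning figures

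*SAP*

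**What the plan says.** SAP 2.4.1 defines the endpoint as "Time to response, defined as the time from first dose of Obinutuzumab to first documented response as assessed in clinical routine". Its censoring rule begins "Patients without response at the time of analysis and patients who are lost to follow-up will be censored", and the date used is that of the last tumour assessment. The rule does not separate patients who progressed or died without responding from those still under follow-up or lost.

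A further sentence covers patients who were never reassessed: "Patients without post-baseline tumor assessments will be censored at the time of their baseline visit unless death occurs prior to their first scheduled tumor assessment". It lifts baseline censoring for early deaths but does not say what replaces it. Protocol 6.3.2 has the same rules.

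SAP 3.2.2 lists time to response among the outcomes summarised by quartiles and Kaplan-Meier plots with 95% confidence intervals, and adds: "Estimates for the survivor functions for all time to event endpoints will be obtained by the Kaplan-Meier approach". Protocol 6.7.1 agrees. The overall response rate is handled differently: "Response rates (ORR, CR, CR30 and rate of patients with stable disease) will be presented with the number and proportions of responders and non-responders", with exact intervals.

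Neither document mentions cumulative incidence or competing risks, or restricts time to response to responders. SAP 3.4 states: "No sensitivity analyses are planned".

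**The concern.** Kaplan-Meier treats a censored patient as having the same future chance of response as those still at risk, and passes that patient's weight on to them. This is reasonable for a patient lost to follow-up. It is not reasonable for one who died without responding, or whose disease progressed on the treatment being evaluated. Such a patient will not contribute a first-line response, so the estimate can only move upwards.

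The consequence is limited to the upper part of one secondary curve and its interval. The curve can end above the proportion of the same effectiveness population who ever responded. A reader comparing the plot with the response rate would see two different figures for one quantity.

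**Working it through.** **The plan's own figures.** Neither document states a figure for time to response or a planning response rate. The stated precision for POD24 does reproduce: 39/300 gives an exact 95% interval of 9.41% to 17.34%, width 7.93% against the stated 7.9%. It does not bear on this point.

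**Inputs from the documents.**
- Response rate 88.5%: the GALLIUM obinutuzumab arm, Protocol Section 4. Used as an illustration only.
- Assessments at about 3, 6 and 12 months: note j of Protocol Appendix 2 and SAP Appendix 1.
- 2-year PFS of 90%: note in Protocol 6.7.5. Expected POD24 of 13%: SAP 2.6.

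**Assumptions.** First response is documented at months 3, 6 and 12 in 60, 25 and 3.5 of every 100 patients (total 88.5). Of the non-responders, a have their last assessment at month 3 and b at month 6. The rest are assessed to month 12 or later.

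**Formula.**

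1−KM = 1 − 0.40 × [1 − 25/(40 − a)] × [1 − 3.5/(15 − a − b)]

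The cumulative incidence of response is 88.5% in every row.

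| a, b (per 100) | Survivor function after month 12 | 1−KM |
|---|---|---|
| 0, 0 | 0.40 × 15/40 × 11.5/15 = 0.1150 | 88.5% |
| 0.5, 1 | 0.40 × 14.5/39.5 × 10/13.5 = 0.1088 | 89.1% |
| 1, 1 | 0.40 × 14/39 × 9.5/13 = 0.1049 | 89.5% |
| 1, 2 | 0.40 × 14/39 × 8.5/12 = 0.1017 | 89.8% |
| 3, 3 | 0.40 × 12/37 × 5.5/9 = 0.0793 | 92.1% |
| 3, 4 | 0.40 × 12/37 × 4.5/8 = 0.0730 | 92.7% |

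The first row shows that there is no bias when no non-responder leaves before the latest first response.

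**Which rows fit the planning figures.** Under a constant hazard (an assumption), 2-year PFS of 90% implies 1 − 0.90^(6/24) = 2.6% progressed or dead by month 6. POD24 of 13% implies 1 − 0.87^(6/24) = 3.4%. Both include patients who had already responded. Early exits without response of 1.5% to 3% are compatible with these. Exits of 6% to 7% are about twice as many or more.

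**A second layout.** Take 266 responders of 300 (88.7%), 200 first documented at month 3 and 66 at month 6, with c non-responders last assessed between the two:

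1−KM = 1 − (100/300) × (34 − c)/(100 − c)

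- c = 8 (2.7% of patients): 90.6%, an excess of 1.9 points.
- c = 14 (4.7%): 92.2%, just above the upper exact limit for 266/300 (84.5% to 92.0%).

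Placing all early exits before the second assessment therefore raises the excess to about 2 points for a similar number of patients.

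**Quartiles.** In the table, 60% respond at month 3 and at least 85% by month 6 in every row, so no quartile moves. A constant-hazard model (response hazard 0.3 per month, final incidence 88.5%) makes every non-responder fail eventually and is harsher than the planning figures. Comparing cumulative incidence with 1−KM, the lower quartile is 0.98 against 0.96 months, the median 2.46 against 2.31, and the third quartile 5.55 against 4.62.

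**The case against.** The case for leaving the text alone has real force.

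- **Censoring is at the last assessment, not at progression.** Protocol 6.1 collects tumour data "until disease progression, withdrawal of consent, study termination by the Sponsor, or death, whichever occurs first", but only for patients who stop treatment for reasons other than progression. The same section follows all patients for 3.5 years. A progressed non-responder who is still being scanned stays in the risk set and causes none of this bias. This stands and makes the bias conditional. If such a patient later responds to second-line treatment, that is a separate problem.
- **Few patients are involved.** Entry requires at least two cycles, so the earliest failures are already absent. Non-responders with lasting stable disease who are still assessed add nothing. This also stands.
- **The planned numerical summary is quartiles, and response probability is reported separately.** This is largely right for the lower quartile and median. It does not cover the plotted upper curve and its interval.
- **Protocol 6.7.1 promises further work on bias and names informative censoring.** This does not resolve the point. SAP 3.2 does not carry the commitment over, and SAP 3.4 plans no sensitivity analyses.

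A reader might infer that the curve is bound to contradict the response rate, by 4 points or more. That requires something like the last row of the first table, with all 11.5% of non-responders progressing or dead by month 12. This exceeds the roughly 10% of patients with any PFS event by month 24 on the protocol's own figure, and leaves no non-responder with stable disease. The documents do not support it.

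**Conclusion.** The point holds as a conditional and small upward bias. As written, the rule treats competing events as ordinary censoring, and nothing elsewhere in the SAP corrects it. With the cited 88.5% response rate and 1.5% to 3% of patients leaving early without response, the curve ends at about 89.1% to 89.8%, an excess of roughly 0.6 to 1.3 points. The excess is nearer 2 points if those exits all come before the second assessment. An endpoint of 92% or more needs early failure well above the planning figures. The effect lies in the upper curve and plateau; the lower quartile and median barely move.

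These sizes rest on assumed timings of response and failure, which the documents do not give, and on a trial response rate that is not this study's planning value. The fair comparison is with the proportion who ever responded in the same effectiveness population, since the response rate is also reported at several time points. Time to response is a secondary endpoint in an estimation study, and the primary endpoint and sample size are unaffected. This is a cheap improvement, not a threat to the study's conclusions.

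**What to change.** In SAP 2.4.1 and 3.2.2:

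- Estimate time to response by the cumulative incidence function (Aalen-Johansen), with progression, death or new anti-lymphoma therapy before response as competing events.
- Count a death before the first scheduled tumour assessment as a competing event, so that the exception for early deaths is no longer open. Treating it as an event of the endpoint would overstate response further.
- Censor only patients still under first-line follow-up without response, or lost.
- Optionally, give the median time to response among responders beside the response rate.

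If nobody is lost before the latest first response, the new curve ends at the observed proportion of responders.

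The cost is a small SAP text change and a different analysis call in R, using progression, death and new-therapy data that are already collected. Protocol 6.3.2 and 6.7.1 should be aligned at the next amendment, which under Protocol Section 3 goes through ethics committee approval. The plotted curve becomes slightly less favourable.
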